3.0 BACKGROUND

3.1 NON-SMALL CELL LUNG CANCER

Lung cancer is the number one cause of cancer related death among both men and women in the United States. Approximately 200,000 new cases of lung cancer are diagnosed each year, representing 15% of new cancer cases. ^{1,2,3}

Nearly 180,000 people died of lung cancer in 2003, comprising 30% of all cancer deaths. At present the one-year survival is 40% while the overall five-year survival for all stages of lung cancer remains at only 14%. ^{4,5}

Following surgical resection for a Stage I non-small cell lung cancer there is a one-year survival of more than 80% and a five-year survival between 60-70%.^{6,7} The best one year and five year survival data for Stage I non-small-cell lung cancer is achieved with surgical intervention. Stage I non-small cell cancer requires that no regional lymph nodes or mediastinal lymph nodes be involved. The tumor must be greater than 2.0 cm from the carina. T1 tumors in Stage I are less than 3.0 cm and do not involve the visceral pleural while T2 tumors are greater than 3.0 cm or invade the visceral pleura.

Presently patients with probable Stage I non-small-cell lung cancers are offered operation if their preoperative staging, which usually includes MRI (magnetic resonance imaging)^{8,9,10} of the brain and PET scan to rule out liver, bone, adrenal or mediastinal lymph nodes are negative. While operation results in the best long-term outcomes for Stage I lung cancer as opposed to radiation

and/or radiation-chemotherapy protocols, the thoracotomy or less invasive thoracoscopic approach does cause morbidity and mortality.

There is a 1-4%^{11,12,13} mortality for thoracotomy and morbidity includes arrhythmias, wound infection, hemothorax, broncho-pleural fistula, pneumonia and deep venous thrombosis. In addition, the spreading of the intercostal spaces with thoracotomy or the insertion of intercostal trochars with manipulation of the intercostal nerves for thoracoscopy causes considerable discomfort.¹⁴ Pain management is a significant problem following thoracotomy or thoracoscopy and postoperative pain is primarily managed with epidural catheter and infusion of Lidocaine, Demerol or morphine. Other techniques of pain management include intercostal nerve block during the thoracotomy or insertion of a catheter along the intercostal nerves to intermittently inject an anesthetic agent.

If a percutaneous CT-guided therapy could achieve the same results as an operative approach, it would revolutionize cancer treatment and options. In addition, it would markedly improve the pain control and the morbidity associated with thoracoscopy or thoracotomy. The percutaneous cancer treatment would have to demonstrate that the ablation efficacy is the same as with a thoracotomy while minimizing collateral damage and overall morbidity.

Percutaneous ablation would be an alternative treatment for patients who could not tolerate lung resection because of marked impairment of pulmonary function secondary to smoking.^{15,16,17} Other medical contra-indications including recent myocardial infarction or impaired cardiac status would also allow patients who would not be surgical candidates to receive an equally efficacious treatment. Presently, the patient who is not a surgical candidate would receive chemotherapy or a chemotherapy-radiation protocol. These protocols have multiple side effects due to the chemotherapeutic agent and the radiation therapy delivered to the underlying organ. In addition, they require multiple visits to the radiation suite and the chemotherapy unit. The cryotherapy option is a single treatment option administered as an outpatient, or overnight monitoring.

With the introduction of endobronchial and trans-esophageal ultrasound guided biopsy of mediastinal lymph nodes, one could envision treating the peripheral tumor with cryotherapy and staging the mediastinal nodes in a relatively non-invasive manner. This would allow accurate pathologic staging rather than image based staging and a true comparison of surgery, radiation and /or cryotherapy for similar stage lung cancers.

3.2 METASTATIC LUNG CANCER

A second cohort of patients who would be candidates for the protocol are those with limited (≤ 3) number of metastatic lesions, each less than 3.0 cm and resectable. These patients would satisfy the usual preoperative criteria for operations with metastatic neoplasms to the lung.¹⁸

These patients would meet the criteria that removal of all metastatic lung tumor is being achieved and retain good pulmonary function after surgical removal of the affected tissue. The primary tumor must have been treated or be under control. The definition of local control will vary depending on the primary tumor. These patients must have absence of metastases to other locations. The final requirement is that lung metastases have no alternative treatment available. Patients that meet these criteria would be offered the option for percutaneous cryotherapy.

Three weeks after treatment the patient would receive a CT scan and then undergo surgical resection with the mediastinal resection for staging purposes. Many authors have reported a five-year disease-free survival in the 30-45% range with resection¹⁸ of pulmonary metastases using these criteria.^{19,20,21}

3.3 CRYOTHERAPY

Enthusiasm still exists for radiofrequency ablation (RFA) in multiple organs despite relatively high recurrence rates in lung²²⁻²⁴ that we have not encountered with cryotherapy in our ongoing human trials at our institution. RFA appears particularly prone to failure for tumor sizes above 3cm and abutting adjacent vasculature. If a tumor abuts a vessel >3mm, RFA appears to produce a relatively consistent recurrence rate of ~50% in liver²⁵, kidney²⁶ and lung²²⁻²⁴. Despite these problems, the relatively low morbidity compared to resection and the improved survival rates²⁷⁻²⁸ makes RFA an accepted treatment option. The apparent ability for cryotherapy to be more capable of thorough ablation even near vessels may require more definitive tissue confirmation in our proposed resection study.

Cryotherapy with the use of cytotoxic freezing temperatures for cancer treatment was first used in the early 1900's. Percutaneous cryotherapy was initiated when smaller probes were able to be accurately placed and monitored using ultrasound guidance for liver and prostate tumors²⁹⁻³¹. Intraoperative ultrasound was able to monitor the leading edge of the ice ablation zone with millimeter accuracy. The ability to instantaneously initiate and terminate both freeze and thaw cycles with Argon gas systems also made cryotherapy more controllable. Cryotherapy for hepatic and prostate lesions has since become well established. Our center has also become the leading site for percutaneous cryotherapy of nearly any organ, including publications for breast, renal and lung tumors³²⁻³⁴.

Percutaneous cryotherapy is administered with the application of 1.7 or 2.4 mm diameter cryo probes. Ice ball sizes vary between 1.5 and 3.0 cm in diameter, dependant on the vascularity or fibrous content of the tissue. For an example, tumors within the cirrhotic liver, which contains significant collagen fibers, or fibrous lesions of the prostate may require more numerous and closely spaced cryoprobes (e.g., <1.5cm apart) to adequately achieve cytotoxic temperatures (-40°C). In addition, the high heat low load and/or low conductivity of lung tissue has been recently confirmed in an animal model, whereby cryoprobes spaced 2.0 cm apart did not generate lethal temperatures at the midpoint between the probes³⁵.

Lengths of the ice ball are consistent with both probe sizes and are approximately 4.5 cm. Maximal lethal ice dimensions for even multiple probes in high heat load tissue require a freeze/thaw/refreeze cycle of at least 15:10:10 minutes respectively. The general rule is that more than one cryotherapy probe is required for each centimeter of tumor diameter. A 2-3 cm lung tumor may thus require 3-4 probes, especially if the tumor abuts a vessel >3mm in diameter. Masses less than 2.0 cm in size may be easily treated by bracketing the tumor with two probes, rather than relying upon a highly accurate central single probe placement. However, if a tumor approaches 2 cm and lies near major vessels, even 3 cryoprobes may be needed with current technology to assure thorough lethal ice along all margins abutting vessels. Ice ball margins of multiple cryotherapy probes coalesce to form a larger volume as seen in Figure 1³⁴.

The patients selected for this protocol will not need multiple planning sessions and CT scans to assess tumor position in relation to other organs. Multiplanar reconstruction of the tumor to be

treated and the mapping of the appropriate probe requirement can be determined from the baseline CT scan. CT scan documentation of ice progression is required during the procedure as well as scanning after completion of the first and second thaw cycles.

Cryotherapy has achieved areas of complete necrosis without basic disruption of the underlying anatomic architecture since it is relatively sparing of collagen. In addition, the margins achieved with cryotherapy are more regular, thinner and better defined than with RFA. The radiotherapy appears to destroy underlying anatomic architecture or "melts" the tissue. In addition, the patients who undergo radiofrequency ablation require significantly more sedation as the burn from radiofrequency is quite painful and often results in overnight hospitalization for pain control for at least 24 hours.³⁶

Significant numbers of patients who have developed lung cancer or secondary metastatic disease are not candidates for lung resection because of inadequate pulmonary function. These patients can presently be treated only with radiation or chemotherapy. One benefit of evaluating cryotherapy as the initial treatment for primary lung or metastatic disease is that patients previously considered unresectable would now be able to achieve a "non-surgical" resection using cryo surgery.

3.4 RATIONALE

Many patients with non-small cell lung cancer are not candidates for surgery secondary to inadequate pulmonary function for resection or poor cardiopulmonary reserve. The location of the tumor such that resection would require removal of vital structure (ex. superior vena cava, thoracic aorta) could also rule out a surgical approach.

In patients with metastatic lung disease, the ability to treat patients without thoracotomy would be an advantage since they frequently have recurrences requiring multiple thoracotomies. These patients also would benefit from preservation of as much lung tissue as possible, which would be maximized with a non-resective localized technique. Patients with metastatic lung cancer often have multiple lesions and are not a candidate for lung resection as they would have inadequate pulmonary function after operation. The impairment of cardiopulmonary reserve could rule out their candidacy for surgical resection.

A percutaneous approach, which would have comparable results to resection without its attendant morbidity and mortality, would also be attractive. In addition, an outpatient percutaneous approach would decrease hospitalization and overall healthcare costs. If similar treatment outcomes could be achieved on an outpatient basis with a several-hour treatment rather than a five to six day hospitalization required for thoracotomy or thoracoscopy, this would be a major advantage in medical costs.

Recent data has demonstrated that percutaneous cryotherapy can ablate lung tumors without loss of underlying architecture including blood vessels³². These techniques have also been successful in terms of ablating pain and have been used for patients with intractable discomfort.³² Cryotherapy of the lung has usually been utilized only as a treatment of last resort in patients who cannot be offered surgical resection because of limited pulmonary status, cardiopulmonary reserve, advanced metastatic disease, advanced local disease and with debilitating pain syndromes³².

There are no studies on the efficacy of percutaneous cryotherapy of lung tumors other than chest CT scan or by utilizing PET scan to demonstrate that no residual tumor is present.³⁷ There is no study that histologically demonstrates that the percutaneous cryoablation technique has been able to kill all viable tumor cells, including the potentially misleading breast cancer data which reports insufficient ablation of tumors >1.5 cm but only used 1 probe in all cases³⁸.

This study would resect the ablated lung tissue after a sufficient period of time to assure thorough necrosis by standard hematoxylin and eosin stains (i.e., >1 day), but not so long after cryotherapy that central necrosis can not be differentiated from healing rim (i.e., <60 days). This allows greater flexibility in the recruitment of patients surrounding their scheduled resection. The resected ablation zone will be measured to compare the average diameter in three dimensions with the CT scan dimensions. The diameter of the necrotic tumor and the ablated zone will be measured and compared with these areas on the CT scan. The ablative zone's regions of enhancement or nodularity (i.e., possible residual cancer) will be compared with regions (anterior, posterior, superior, inferior, medial and lateral) from the pathologic analysis of the tumor, including effects upon any adjacent bronchi and vasculature. We expect that all tumor will be eradicated with cryotherapy, but would define success as more than 75% of analyzed tissue being negative for cancer. Radiofrequency ablation frequently leaves residual tumor and recurrence rates range from 12-58%²²⁻²⁴ depending on tumor size and vessel proximity. Our hope is that the percutaneous cryoablation technique will show more thorough destruction of cancer cells.

The usual clinical scenario is that the patient who is receiving percutaneous cryotherapy does not have an operation or cannot have an operation. This study would give us the unique opportunity to resect the tissue, which has received cryotherapy, and determine whether this is a viable treatment option as a primary treatment modality rather than as a last ditch treatment, or treatment of last resort.

4.0 PATIENT SELECTION

4.1 Eligibility Criteria

1. Patients must have histologically or cytology-demonstrated non-small cell carcinoma or metastatic lung disease. The diagnosis can be made by CT – guided needle biopsy, bronchoscopic biopsy, or transbronchial biopsy. Only patients who have a definitive diagnosis of cancer can be enrolled.
2. Patients must have measurable disease defined by one peripheral lung lesion that can be accurately measured in at least one dimension with the average diameter \leq 3.0 cm on conventional CT scan techniques.
3. Patients with metastatic lung disease must have no more than 3 peripheral lung lesions (each \leq 3.0 cm in average diameter) which have not been treated with radiation or chemotherapy since the new metastatic lesion appeared. Lung must be the only site of metastases.
4. Patients may not have received any prior chemotherapy or radiotherapy for this particular lesion prior to treatment with percutaneous cryotherapy.

5. Patients must be 18 years of age or greater
6. Patients must have adequate pulmonary function tests (as determined by the treating physician) to tolerate either the lobectomy or wedge resection required. This would entail that the patient have a FEV-1 following resection of at least 1.0 L/sec and pre-operative diffusing capacity of >50%.
7. Patient would have had a pre-therapy CT scan of the chest and PET scan as a baseline.
8. The patient must have neutrophil count of greater than 1,500 c/mL, a platelet count greater than 75,000 c/ml and INR \leq 1.5.
9. Patients with metastatic lung disease must have their primary tumor under local control and have no evidence of metastatic disease other than the lung.
10. The patient must have the ability to understand and willing to sign a written informed consent document.
11. The patient must be registered with the Clinical Trials office at the Karmanos Cancer Center/Wayne State University.

4.2 Exclusion Criteria

1. The inability or unwillingness to interrupt aspirin, or other platelet inhibiting drugs, Coumadin or heparin prior to the study.
2. Uncontrolled or concurrent other illnesses, including active infection, heart failure, unstable angina, cardiac dysrhythmia, psychiatric illness or a social situation that would limit compliance with the study requirements.
3. Patients must agree to follow an acceptable method of birth control while participating in this study.
4. Women who are pregnant or lactating.
5. Patients in other ongoing experimental studies.

4.3 Inclusion of Women and Minorities

Both genders and members of all races are eligible for this trial.

4.4 Registration Procedures

All patients will be registered at the Clinical Trials Office (CTO) of the Karmanos Cancer Center/Wayne State University by [name] or [name].

Registration and Data management for the protocol will comply with all Karmanos and National Cancer Institute regulations for research studies. The study coordination will be undertaken by trained personnel who meet the minimum criteria espoused by Karmanos

Cancer Institute and the National Cancer Institute. The personnel will include [name] and her designees who are currently providing these services for [name] present cryotherapy protocols, and [name], Karmanos surgical PA who works in the cancer institute, the operating room and clinic with [name].

5.0 TREATMENT PLAN

All patients who have been diagnosed with primary Stage I lung cancer or limited metastatic disease, confirmed by percutaneous transthoracic needle biopsy or transbronchial biopsy will also have a CT scan of the chest, MRI of the brain and a PET scan. All patients will have no evidence of cerebral disease, no evidence of metastatic disease by the PET scan or the CT scan. This will include no evidence of satellite lesions on the CT scan of the chest, no mediastinal lymph nodes greater than 1.5 cm. There will be no hepatic or adrenal masses noted. MRI of the brain will not demonstrate evidence of metastatic disease. PET scan may show only significant uptake in the primary lung lesion. There will be no areas that have SUV of greater than 2.5 in any location other than a primary lesion considered under control in the metastatic subgroup. The lesion on the lung CT scan must be in the peripheral third of the lung.

The patients with metastatic lung cancer will have a solitary or limited number (≤ 3) of lesions less than 3.0 cm diameter. They will have prescreening MRI of the brain, which demonstrates no evidence of disease, the chest CT scan and PET scan will demonstrate no evidence of other metastatic disease and control of the primary tumor. Patients will then undergo treatment with percutaneous cryotherapy to the lesion. This will be performed on an outpatient basis.

The technique for local anesthesia will be 1% Lidocaine for the initial skin injection with 1% Lidocaine with Epinephrine (1:1000) for deeper injections. This will minimize bleeding and increase the duration of the Lidocaine. A 3.0-4.0 cm wide path of local anesthesia for each probe will be created by angulating the injection in several directions all the way to the tumor site. Intercostal nerve blocks will be achieved as needed with Lidocaine on each side of the lesions and on both sides of the affected rib.

The cryotherapy equipment (Endocare, Inc., Irvine, CA) will utilize application of 1.7 and/or 2.4 mm diameter cryoprobes. The ice ball size for these probes will vary between 1.5 – 3.0 cm in diameter depending on the vascularity and fibrous content of the underlying tissue and the tumor. The length of the ice ball will be consistent with the probe size at approximately 4.5 cm. Depending on the size of the tumor, a cluster of cryoprobes may be required to adequately achieve cytotoxic temperature (-40° C). The individual probes will require a freeze/thaw/refreeze cycle of up to 15/10/10 minutes respectively. The use of a triple freeze will be at the discretion of the interventional oncologist, whereby the first freeze: thaw is of short duration to facilitate further ablation. The general rule is that there is more than one cryotherapy probe for each centimeter of tumor diameter as previously noted.

A central guidance needle (20 gage, 15 cm length) is first placed in order to define the ideal course and angulation. The cryoprobes are then placed with minimal repositioning and secondary tissue disruption. Saline injections of the overlying skin will prevent ice necrosis from extending into the epidermal layer as needed.

Cryotherapy procedures currently utilize the Siemens Somatome Plus 4 with the Care Vision fluoroscopy package. The patient will have an initial CT scan to assess tumor position in relation to adjacent tissue while he or she is placed in the anticipated prone or decubitus position for the procedure. Multi-planar reconstructions will be performed to map the approach and probe requirements. CT documentation of the ice ball progression during the procedure will include scans after the first and second freeze cycles. The CT image has better resolution than CT

fluoroscopy images and allows multiplanar reconstructions. The best final image on the final ice dimensions are produced by limited spiral scans after probe removal which eliminates the scatter artifact from the cryoprobe.

Approximately 3 weeks after completion of the percutaneous cryotherapy the patient will receive a CT scan of the chest. The CT scan will assess tumor dimension as well as any residual changes in the treated lung.

The patient will then undergo a standard thoracotomy for lobectomy for the primary lung carcinoma or a limited wedge resection for metastatic lung cancer. The resected tissue will be forwarded to pathology for analysis of remaining tumor. The patients will also have mediastinal node dissection at the time of operation, a standard staging procedure. The lymph node stations will also be assessed for residual tumor. Lung parenchyma surrounding the area of cryotherapy will also be assessed for any residual damage from the cryotherapy probes and treatment.

The histological analysis of the lung, tissue will then be compared with the CT scan. If there is any residual tumor, this will be correlated with the CT scan. In addition, the lung which had been resected will be assessed for damage from the cryotherapy technique.

Patients will have standard follow-up studies as per their primary lung oncologist. The patient will be requested to have a follow up CT scan of the chest and PET scan at six months for their long term follow up.

In addition to patients being followed by the treating physician at as needed clinic visits patients will be followed yearly for survival.

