5.1 Concomitant Medication Therapy

Patients will be instructed to take Prednisone to prevent/alleviate any acute inflammation. The steroid should be taken:

20mg BID on the day of the cryotherapy procedure

20mg BID on the day after the procedure

20mg BID two days after the procedure

20mg AM and 10mg PM three days after the procedure

10mg AM and 10mg PM four days after the procedure

10mg five days after the procedure

5mg six days after the procedure

STUDY CALENDAR

	Pre-Cryotherapy	Cryotherapy	Week 1 ^H	Week 2 ^H	Week 3	Thoracotomy ^J	Month 6
Diagnosis	X						
Informed Consent	X						
Demographics	X						
Medical History	X						
Physical Exam ^G	X ^C						
Chest X-ray	X ^B	X	X	X			
CT scan of chest	X ^B				X ^I		X
PET scan	X ^A						X
MRI of brain	X ^D						
Pulmonary Function Tests (PFTs)	X ^D				X ^I		
EKG	X ^D						
CBC w/differential	X ^C						
Chem-7 ^F , alkaline phosphatase, SGOT, bilirubin	X ^C						
INR	X ^E						
Pregnancy test, urine or serum	X ^E						
Histology						X	

B: Must be performed within 42 days of cryotherapy

C: Must be within 6 weeks of cryotherapy

D: Must be within 12 weeks of cryotherapy

E: Must be within 1 week of cryotherapy

F: Chem-7 includes BUN, creatinine, glucose, and electrolytes

G: Physical exam to include heart, rate, blood pressure, respiratory rate, temperature and documentation of concurrent medication

H: +/- 2 days

I: 2-53 days following percutaneous cryotherapy; within 7 days of planned thoracotomy

J: Less than 12 weeks from percutaneous cryotherapy

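### Section 5.0 gives the epinephrine in the deep local anesthetic as 1:1000, which is 1 mg/mL if it is the final mixture and leaves the final strength unstated if it is a stock

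*Combined protocol and SAP*

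**What the plan says.** Section 5.0 describes the local anesthesia in a few sentences. For the skin: "The technique for local anesthesia will be 1% Lidocaine for the initial skin injection". For the tissue below it, the preparation is "1% Lidocaine with Epinephrine (1:1000) for deeper injections". The next sentence gives the purpose: "This will minimize bleeding and increase the duration of the Lidocaine". The extent of the infiltration follows: "A 3.0-4.0 cm wide path of local anesthesia for each probe will be created by angulating the injection in several directions", continuing down to the tumor. Intercostal nerve blocks are added when needed, and there only lidocaine is named.

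The number of paths depends on the number of probes. Section 5.0 states: "The general rule is that there is more than one cryotherapy probe for each centimeter of tumor diameter as previously noted". Section 3.3 agrees. It allows two probes for masses under 2.0 cm, says that as a tumor near major vessels approaches 2 cm "even 3 cryoprobes may be needed with current technology", and adds: "A 2-3 cm lung tumor may thus require 3-4 probes".

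Epinephrine is named only in that one sentence of Section 5.0. No volume, dilution step or maximum dose accompanies it. Section 5.1, the concomitant-medication section, deals only with prednisone, starting with "20mg BID on the day of the cryotherapy procedure".

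**The concern.** A ratio strength of 1:1000 is a definite concentration, and the sentence presents it as part of the preparation to be injected. It names the mixture, says where it goes and says what it achieves. On that reading, an operator who follows the text literally injects 1 mg of epinephrine with every mL, across a path several centimeters wide, once per probe.

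The alternative is that 1:1000 describes a concentrated stock added to the lidocaine. The text then omits the step that turns it into an injectable strength, and the operator must supply a number the plan does not contain.

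What is at stake is patient safety, not inference. The procedure is described as outpatient in Section 5.0, and as outpatient or with overnight monitoring in Section 3.1. The specific adverse events listed in Section 6.0 are pneumothorax, hemothorax, hemoptysis and nerve damage; none relates to the anesthetic. The only entry in the study calendar for the day of cryotherapy is a chest X-ray. Routine procedural monitoring may well take place, but the plan does not describe it.

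**Working it through.** The figure 1:1000 is a written specification and is not derived from other inputs, so there is no calculation of the plan's to reproduce. The check is a unit conversion.

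**Inputs from Section 5.0:** lidocaine 1%; epinephrine 1:1000; more than one probe per cm of tumor diameter. **Not given anywhere:** volume per path, total volume, dilution factor, maximum epinephrine dose.

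**Step 1, concentrations.** A strength of 1:R by weight in volume is 1 g per R mL, or 1000/R mg/mL.

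- Epinephrine 1:1000: 1000/1000 = 1 mg/mL.
- Lidocaine 1%: 1 g/100 mL = 10 mg/mL.

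**Step 2, final-mixture reading.** Epinephrine in mg = 1 mg/mL × volume in mL, so the dose in mg equals the mL injected. Lidocaine to epinephrine is 10:1 by mass at any volume.

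**Step 3, stock reading.** If the stock is diluted by a factor D, the final strength is 1/D mg/mL. D is not written. The values below are assumptions for illustration only:

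| Assumed D | Final strength (mg/mL) | As a ratio |
|---|---|---|
| 10 | 0.1 | 1:10,000 |
| 100 | 0.01 | 1:100,000 |
| 200 | 0.005 | 1:200,000 |

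These three differ by 0.1/0.005 = 20-fold. That range reflects the values chosen, not anything in the plan.

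**Step 4, number of paths.** Taking more than one probe per cm literally: above 1 at 1 cm means at least 2; above 2 at 2 cm means at least 3; above 3 at 3 cm means at least 4. Cohort B allows up to three lesions, which could add paths. This shows that the injection is repeated; it does not give a dose.

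**Step 5, sensitivity to volume.** The volume has to be assumed. With a total of 5, 10, 20 or 40 mL, the final-mixture reading delivers 5, 10, 20 or 40 mg of epinephrine. At 1:100,000 (also assumed) the same volumes deliver 0.05, 0.1, 0.2 or 0.4 mg, and at 1:200,000 they deliver 0.025, 0.05, 0.1 or 0.2 mg. The gap is 100-fold or 200-fold at any volume, because volume cancels in the ratio.

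**The case against.** The strongest reply accepts the quotation and the arithmetic and disputes the weight given to them. It has four parts.

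- **Harm is not shown from the documents.** They contain no epinephrine limit and no injected volume, so the arithmetic proves 1 mg/mL and not a clinical consequence. This stands: that 1 mg/mL is unsuitable for wide infiltration is a premise from general pharmacology and is stated here as an assumption. It does not rescue the text, because the alternative reading leaves the strength undefined.
- **The reading is not settled.** Correct. The sentence favors the final mixture, but the documents do not show the intended strength. The certainty attaches to the notation, not to any patient having received that dose.
- **Safeguards exist.** The site reports ongoing human cryotherapy trials (Section 3.3). Section 4.2 excludes uncontrolled or concurrent heart failure, unstable angina and dysrhythmia. Section 9.4 has a rule for serious adverse events of any type, and Section 10.0 provides monthly review. Experience and exclusions lower the likelihood of harm; the last two act only after an event. None changes the written strength.
- **This is ancillary drug detail.** Prednisone is listed in mg because patients take it themselves, and the nerve blocks in the same paragraph carry no concentration at all. The comparison with prednisone is therefore weak support. The better argument is that the plan chose to state a strength here, and a stated strength must be right.

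The illustrative dilutions and the probe counts add scale, but the finding does not depend on them.

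**Conclusion.** The concern holds and should be treated as a required correction. As written, the deep anesthetic contains 1 mg of epinephrine per mL if the ratio describes the injected mixture, and has no stated final strength if it describes a stock. Neither gives the operator a usable strength that can be relied on as safe, and nothing else in the document resolves the point.

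Confidence is high on the conversion and on the absence of any correction. The judgment that this matters clinically rests on the pharmacological assumption stated above and on the possibility that staff follow the text literally. No total dose is claimed. The finding has no bearing on the precision table or the safety monitoring limits.

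**What to change.** In Section 5.0, replace 1:1000 with the final epinephrine concentration of the mixture actually injected, confirmed with the investigators and pharmacy and written in mg/mL or µg/mL. If 1:1000 is a stock, write the dilution step and the concentration that results. No replacement value is proposed here, because the documents do not show what was intended. A maximum epinephrine dose for the deep injections would be a sensible addition but is optional.

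The cost is a one-sentence amendment, with no change to sample size, visit schedule, endpoints or analysis.
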